- A 3.8 ml (¾ tsp) blood sample will be collected for anti-FVIII chromogenic Nijmegen Bethesda inhibitor assay (CBA) (plasma), antigen-specific (FVIII) T cell ELISPOT assay (PBMC), trough FVIII chromogenic activity (aliquot of plasma), and a sample (aliquot of plasma) stored for future studies (for hemophilia genetic or immunologic studies). All samples must be drawn prior to the *Eloctate* with/without *Emicizumab* doses.

The total blood volume for all tests is 22.8 ml (4½ tsp) during the 48-week study. Monthly blood sampling will be 3.8 ml (¾ tsp). Amounts of blood drawn will be less for children weighing less than 14 pounds. The Appendix detailing timing of visits and blood draws is attached on the last page of this protocol.

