3.2 Research Design and Methods

This is a 48-week outpatient, randomized phase III clinical trial that employs Bayesian Platform design to assess inhibitor eradication in patients with severe hemophilia A, FVIII <0.01 IU/ml, and a current or past high-responding inhibitor (anti-FVIII >5.0 B.U.), ITI-refractory or ITI-naive. Because hemophilia is a rare disease, we incorporated Bayesian Platform design and will use historical and prospective ongoing clinical trial data on inhibitor formation (Bayesian "priors") to efficiently use rare patients and increase power. The Inhibitor Eradication Trial is linked to the Inhibitor Prevention Trial, and the trials are integrated so there is efficiency and economy, using the same HTCs, staff, frequency of blood sampling, visits, data collection, and lab assays. The Eradication Trial is a randomized phase III open-label trial designed to evaluate the efficacy of *Eloctate* immune tolerance induction (ITI) (100 IU/kg every other day) plus weekly *Emicizumab* 1.5 mg/kg weekly (after a 4-week induction) vs. Eloctate ITI alone (100 IU/kg every other day), to eradicate inhibitor formation in adults or children with severe hemophilia A and current or past high-responding inhibitors to FVIII, anti-FVIII \geq 5.0 B.U. Approximately 2-4 children or adults with severe hemophilia A and inhibitors will be recruited at each HTC. The study drugs will be administered to each subject for up to 48 weeks. *Eloctate* will be given either by weekly intravenous infusion over 5-10 minutes, and (Eloctate) will be given by weekly subcutaneous injection over 1-2 minutes. For treatment of breakthrough bleeds, for safety reasons, rFVIIa will be given by intravenous infusion over 5-10 minutes at 90 mcg/kg per standard of care, at MD discretion, or if the inhibitor titer has fallen, additional Eloctate will be given, per MD discretion. The treating physician may be the study physician. FEIBA will not be allowed on the trial as it may result in thrombosis or thrombotic microangiopathy in patients taking Emicizumab. All bleeds and study drug(s) will be recorded by patient or parent/ caretaker for each subject in a patient diary. All randomized subjects will be followed 48 weeks or until they reach the study outcome of inhibitor eradication. Follow-up visits will be monthly until end-of-study, week 48.

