The primary endpoint will be eradication of an inhibitor, defined as anti-FVIII < 0.6 B.U. by chromogenic Nijmegen Bethesda assay (CBA). A local lab anti-FVIII < 0.6 B.U. will be repeated on this sample or, if insufficient, a repeat sample within 7 days, and a second sample obtained within 4 weeks for confirmation. A central lab anti-FVIII < 0.6 B.U. will be repeated within 4 weeks for confirmation. A central lab anti-FVIII < 0.6 B.U. will be repeated within 4 weeks for confirmation. A central lab anti-FVIII < 0.6 B.U. will be repeated within 4 weeks for confirmation. All subjects whose inhibitor is eradicated will remain on study follow-up to week 48. Additional tests will be done, per standard of care, including peak and trough to advise when ITI can be stopped and regular prophylaxis can begin. Subjects whose inhibitor is eradicated, i.e. anti-FVIII < 0.6 B will receive *Eloctate* with/without *Emicizumab*, per physician discretion, to treat or prevent bleeds: if bleeding occurs that is unresponsive to *Eloctate* with/without *Emicizumab*, rFVIIa will be used. FEIBA will not be allowed on this trial for safety reasons.

It is anticipated that 2-4 subjects will be enrolled locally, contributing to the overall study enrollment of 90 subjects at one of up to 41+ participating HTCs. The duration of the study is approximately 48 weeks per subject, with an expectation the study will last up to 7 or more years, subject to enrollment and completion of all procedures. For this study, all study visits will occur at the HTC.

SCREENING VISIT, RANDOMIZATION, AND INITIATION OF ASSIGNED TREATMENT Study Visit 1, Screening/ Baseline Visit, Wk 0

This visit will take place prior to administration of *Eloctate* with/without *Emicizumab* in order to confirm eligibility requirements. Randomization and initiation of treatment may occur at this visit or within 4 weeks of the visit. The following tests or assessment will be performed at the Screening/ Baseline Visit.

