- Blood draw: A 3.8 ml (¾ tsp) blood sample will be collected for anti-FVIII chromogenic Nijmegen Bethesda (CBA) assay (plasma), antigen-specific (FVIII) T cell ELISPOT assay (PBMC), HLA and hemophilia genotype (buffy coat of the plasma sample), trough FVIII chromogenic activity (aliquot of plasma), and a sample (plasma) stored for future studies. All samples must be drawn prior to the study drug dose. Amounts of blood drawn will be less for children weighing less than 14 pounds. The Appendix detailing timing of visits and blood draws is attached at the end of this protocol.
- The samples (all de-identified) and labeled with subject ID number will be processed, frozen, and shipped to a repository in the Coagulation Laboratory at Vitalant, Pittsburgh PA, under the direction of [name]. The inhibitor titer will be run by chromogenic Nijmegen Bethesda (CBA) assay real time, with confirmation on stored aliquots for those testing negative (< 0.6 B.U.). An aliquot of plasma sample will be assessed for trough FVIII chromogenic assay (aliquot of plasma sample). The micriobiome (stool) sample will be shipped to the Vitalant Lab and transported to the microbiome, Vascular Medicine Institute (VMI), Pittsburgh, under the direction of [name]. The PBMC sample will be snap frozen in dimethyl sulfoxide (DMSO) and stored in liquid nitrogen until batch testing for antigen-specific (FVIII) T cell responses by ELISPOT assay in the research laboratory of [name], Uniformed Services of the Health Sciences (USUHS), Bethesda, MD. Samples for future testing (for hemophilia genotype or immunologic studies) will be stored indefinitely.

- Stool sample: A small stool sample will be collected at home to assess genes and bacteria in the gut (micriobiome) and placed in a small tube and returned in a container mailer to Vitalant, and couriered to VMI, Pittsburgh PA.
- After the study physician determines eligibility, the subject will be **randomly assigned to one of the two treatment strategies**, *Eloctate ITI* plus *Emicizumab* or *Eloctate ITI alone*.

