3.5 Study Population

The Inhibitor Eradication Trial will enroll 90 adults and children \geq 4 months of age with severe hemophilia A with high-responding inhibitors (anti-FVIII \geq 5.0 BU) who are ITI-refractory or ITI-naïve, or developed on the Prevention Trial.

The Inclusion Criteria for the Eradicate Trial include children and adults \leq 4 months of age; severe hemophilia A (FVIII < 0.01 U/ml); current or past high-responding inhibitor to FVIII (anti-FVIII \geq 5.0 B.U.), or ITI-refractory or ITI-naive. Exclusion Criteria include acquired hemophilia or any bleeding disorder other than hemophilia A; use of an experimental drug(s); surgery anticipated in the next 48 weeks (except port placement); life expectancy less than 5 years; patient/parent/caretaker unable or unwilling to keep a personal diary of bleeding frequency and study drug treatment, make monthly visits and blood draws; or other illness, condition, or reason in the opinion of the investigator that would make the patient unsuitable for the trial.

Our 2019 survey indicates there are 274 refractory inhibitor patients at 31 HTCs. When combined with 12 inhibitor patients from the Prevention Trial (8x25% plus 52x15% = 12), that is 25% of N=8 Eloctate-treated and 15% of N=52 Emicizumab-treated, for a total 4+8=12, we will achieve 90 inhibitor subjects (78+12) over the 6-year enrollment. With *only* 29% participating, we will enroll 78 refractory inhibitor patients plus 12 inhibitor patients from the Prevention Trial, we will enroll 90 severe hemophilia A inhibitor subjects over the 6-year enrollment period (Table 1).

Inhibitors in 6 yr Prevention Trial	Non-Trial Inhibitors at HTC	% of 6 yr Total for 6 yr Trial	Sample Size, Power for 6 Yr Trial
N=12 (8 x 25% = 4) + (52 x 15% = 8)	N = 274 refractory/untreated	29% of 274 = ~78 in 6 yr	90 (78 + 12) Inhib: β=0.80, α=0.05

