The **Primary Endpoint** is the probability of becoming inhibitor-free by 48 weeks, where the eradication of inhibitor formation is defined as anti-FVIII < 0.6 B.U. by chromogenic Nijmegen Bethesda assay (CBA). We *hypothesize* that tolerance induction with *Eloctate ITI* plus *Emicizumab* is superior to *Eloctate ITI* alone in eradicating inhibitors in children and adults with severe hemophilia A and inhibitors. While both drugs may shorten ITI and even be synergistic, there is equipoise.

Analysis of the Primary Endpoint: We propose to take advantage of prior historical information on inhibitor formation to improve power on the Prevention Trial, and efficient use of inhibitors developing on the Prevention Trial (PRO19040140) to enroll in the Eradication Trial. For the **Eradication Trial**, we propose a Bayesian design and analysis plan to test if *Eloctate* ITI plus *Emicizumab* is superior to *Eloctate ITI* alone. Given the lack of data on either arm, we used two non-informative priors and 1:1 randomization allocation. Non-informative Bayesian priors were used for both arms as there are no published data regarding the time to inhibitor eradication with *Emicizumab* or Eloctate. The time to inhibitor eradication will be compared between the two assigned treatment arms by piecewise exponential survival models to determine the probability of being inhibitor-free at 48 weeks. Monte-Carol Markov-Chains (MCMC) were utilized to determine the posterior probability of the outcome when determining the operating characteristics. At the interim, once 75% of the subjects are randomized, the Bayesian posterior probability that either *Eloctate ITI plus Emicizumab* or *Eloctate ITI alone* is more likely to be inhibitor-free must be at least 99.5% to stop the trial. Assuming the trial did not stop at the interim, then to declare significance at the end of the trial, the Bayesian posterior probability that either arm, *Eloctate ITI*

plus Emicizumab or *Eloctate ITI alone* is more likely to be inhibitor-free at must be 97.9%. This maintains type 1 error at 5%, two-sided, with at least 80% power for superiority if we assume the true condition is that *Eloctate ITI plus Emicizumab* has an inhibitor-free rate of 95% and Eloctate ITI has an inhibitor-free rate of 80%.

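### Local-laboratory negatives can start the primary endpoint with no set test timing, confirming laboratory or event date, so detection time could differ by arm in this open-label trial

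*Combined protocol and SAP*

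**What the plan says.** Section 3.2 (Subjects Developing the Primary Endpoint) and Section 3.6 (Subjects reaching the primary endpoint) define eradication as anti-FVIII below 0.6 B.U. by the chromogenic Nijmegen Bethesda assay (CBA). Both then give two ways in.

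- Local route: "A local lab anti-FVIII < 0.6 B.U. will be repeated on this sample or, if insufficient, a repeat sample within 7 days", plus a second sample within 4 weeks to confirm.
- Central route: a central-laboratory negative, repeated within 4 weeks.

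Scheduled anti-FVIII samples are taken at weeks 0, 4, 12, 24, 36 and 48 in both arms (Sections 3.2 and 3.3, Appendix Schedule of Events) and shipped to the central laboratory, where "The inhibitor titer will be run by chromogenic Nijmegen Bethesda (CBA) assay real time". Section 5.1 counts local as well as central assays among the research procedures that the study pays for, but the Schedule of Events has no entry for local tests.

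The trial is open-label (Sections 1.0 and 3.2). Section 3.6 compares time to eradication between arms with piecewise exponential models and derives the 48-week probability from them. It states that "we used two non-informative priors and 1:1 randomization allocation", with posterior thresholds of 99.5% at the interim and 97.9% at the end. It gives neither the cut points nor any rule for events known only to lie between two tests.

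For the local route, the documents do not say when or how often tests are done, which laboratory confirms a local negative, or which date counts as the event. The local sentence does not restate the CBA.

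**The concern.** Eradication is seen only when someone tests for it. If one arm is tested more often, its eradications are found sooner on average. A model of time to eradication that takes the detection date as the event date then gives that arm a higher hazard and a higher 48-week probability, even when the drugs work equally well. In an open-label trial with no rule for local testing, nothing in the plan prevents such a difference. The effect could go either way: extra tests in the combination arm would favour it, and extra tests in the control arm would hide a real benefit.

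**Working it through.** **Inputs.** From the documents: 90 subjects allocated 1:1, so 45 per arm; 95% versus 80% inhibitor-free by week 48; final threshold 97.9%; scheduled tests as above. Assumed: exponential eradication times, lasting eradication, a vague gamma prior per hazard piece, and either one piece or four 12-week pieces. The assumed extreme is that every subject in one arm also has local tests every 4 weeks and none in the other arm does, with each event dated at the first test after eradication.

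**Step 1: the plan's own power.** The plan says "This maintains type 1 error at 5%, two-sided, with at least 80% power for superiority". The implied hazard ratio is ln(0.05)/ln(0.20) = 1.861. Expected events are 45 × (0.95 + 0.80) = 78.75. Schoenfeld's formula gives √(78.75/4) × ln(1.861) − 1.96 = 2.757 − 1.96 = 0.797, so power is 78.7%, close to the stated 80%. A normal approximation with both Bayesian thresholds gives about 77%. Both figures assume exact event times.

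**Step 2: mechanism, true 80% in both arms.** The weekly hazard is −ln(0.20)/48 = 0.03353, and mean time at risk to week 48 is 0.80/0.03353 = 23.86 weeks. Simulated mean delay from eradication to detection is 5.1 weeks on the schedule and 2.0 weeks with 4-weekly tests; the median detection week is 24 versus 16. Add the delay for the 80% with an event and recompute the single-hazard estimate:

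- Scheduled tests only: 23.86 + 0.80 × 5.145 = 27.98 weeks; 1 − exp(−48 × 0.80/27.98) = 74.7%.
- 4-weekly tests: 23.86 + 0.80 × 2.043 = 25.49 weeks; 1 − exp(−48 × 0.80/25.49) = 77.8%.

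The spurious gap is about 3 points. Simulations gave 3 to 4.

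**Step 3: decisions, by simulation (final rule only).** Entries are the chance of declaring the combination arm superior. The first, second and fourth rows use 10,000, 10,000 and 3,000 trials respectively; the others use 3,000.

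| Truth | Testing | One piece | Four pieces |
|---|---|---|---|
| 80% v 80% | scheduled only, both arms | 1.0% | 1.0% |
| 80% v 80% | extra tests, all of combination arm | 3.6% | 3.9% |
| 80% v 80% | extra tests, half of combination arm | 1.8% | 1.5% |
| 95% v 80% | scheduled only, both arms | 61% | 36% |
| 95% v 80% | extra tests, combination arm | 86% | 71% |
| 95% v 80% | extra tests, control arm | 45% | 20% |

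The nominal one-sided level is 100% − 97.9% = 2.1%. In the second row the control arm wins falsely in 0.4% (one piece) or 0.25% (four pieces), so total error stays near 4% but falls almost wholly on one side. With two pieces, the half-arm case gives 2.0%. Repeat simulations agreed to within about 4 percentage points on power.

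**Step 4: what drives it.** With true 80% in both arms, scheduled versus 4-weekly estimates (single hazard) were 74.8% v 77.6% with visit dates taken as exact, 79.8% v 79.7% with midpoint dates, and 80.1% v 79.8% with an interval-censored likelihood. Raw proportions were 80.4% v 80.0%. The shift therefore needs both unequal testing and detection dates treated as exact.

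**Step 5: if negatives can be transient.** If the 20% who are never eradicated have a confirmed transient negative with probability q per test, 12 tests instead of 5 add 0.20 × [(1 − q)^5 − (1 − q)^12]. For an assumed q of 0.5% to 5%, that is 0.7 to 4.7 points on the proportion itself.

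**The case against.** The strongest reply is that the documents never call local tests extra or discretionary. Local laboratories may simply test blood drawn at the scheduled visits: the stated total of 22.8 ml is exactly six draws of 3.8 ml, and Section 5.1 treats local assays as study procedures. On that reading detection does not differ by arm. The reading is possible, but the text does not require it, and the blood total also leaves no room for the second confirmatory samples that the endpoint needs.

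Several stronger readings are tempting and are not supported:

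- **That one local negative is an event.** A repeat and a second sample are required. Confirmation guards against false negatives; it does not equalise when the first negative is found.
- **That detection rests on local tests.** Both arms share five scheduled central tests after baseline, including week 48, so for lasting eradication the crude proportion is protected.
- **That unblinded investigators order the local tests.** The sentence "The treating physician may be the study physician" follows the text on treating breakthrough bleeds and says nothing about who orders inhibitor tests.
- **That the local route uses another assay.** The sentence before it defines the endpoint by the CBA. The local sentence only fails to restate it.
- **That detection bias is present.** No difference between arms is documented.

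It is also fair to say that the illustration is extreme and that visit dates taken as exact are an assumption, since the plan states no dating rule. With half of one arm tested more often, false wins stay below the nominal 2.1%.

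**Conclusion.** The point holds as a gap in the rules for the primary endpoint. A local negative can start the endpoint pathway, its timing, confirming laboratory and event date are open, and the primary model uses event times in an open-label trial. A difference between arms in local testing could therefore move the result. In the assumed extreme the effect is a false gap of about 3 to 4 points, false wins near 4% for the more-tested arm, and power between about 45% and 85% (one piece) or 20% and 70% (four pieces) for the same true effect. Smaller imbalances do much less, and interval-censored handling largely removes the effect. These figures show direction and size only, because the plan's cut points and simulation settings are not given. The point merits a change because the remedy is cheap and has to be in place before data accrue.

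**What to change.** In Section 3.2 (Subjects Developing the Primary Endpoint) and Section 3.6 (Subjects reaching the primary endpoint), define the primary endpoint as a scheduled central-laboratory CBA result below 0.6 B.U., with a central-laboratory CBA confirmatory sample within 4 weeks, allowed after week 48 when the week-48 draw is the first negative. Date the event at the scheduled draw in both arms. Preferably analyse event times as interval-censored: a common schedule removes the difference between arms, but treating visit dates as exact still costs power (61% against 77% with exact times, one piece). Rerun the operating characteristics under the chosen rule. Keep local results for care and for a sensitivity analysis, and record local tests by arm.

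At the same time, reconcile which stored aliquots are retested: the baseline-visit text in Section 3.2 says those testing negative, and Section 3.3 says those testing positive.

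Cost: mainly wording, since central samples are already taken and run as they arrive. The confirmatory draw should be added to the Schedule of Events, and some subjects will need a sample after week 48. Some eradications will be dated at the next scheduled visit, under the same rule in both arms.

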3.3 Data and Specimen Collection

Data Collection. Data will be collected by the study physician(s) and the HTC research nursing staff. All data required by the study protocol will be adequately documented in the source documents (e.g. hospital records, clinical and office charts, laboratory notes, memoranda, subjects' dairies, evaluation checklists, pharmacy dispensing records, lab assay results, copies or transcriptions certified after verification as being accurate copies, microfilm, magnetic media, subject files, pharmacy and laboratory records). Subject information will be captured and managed by electronic Case Report Forms via web-based electronic data capture by the INHIBIT DCC Data Management System. All information will be stored on their server in a secure database (housed in a locked room). No personal identifiers will be associated with the data. Subjects will be children or adult males of all ages with severe hemophilia A and a current or past high-responding inhibitor, anti-FVIII \geq 5.0 B.U., who fulfill the inclusion and exclusion criteria, and are cared for at one of the up to 41+ participating HTCs. Prognostic factors will be collected at baseline, include age, race, family history of inhibitors, current or past emicizumab use, and past circumcision. Follow-up data will be collected through week 48, including adherence

(diary), bleeds (no., type, location treatment), factor use (dose, date), and if used, central line use or infection (time to, number). Data collected from subjects at baseline and follow-up visits will include demographic, medical, and health information, including site and frequency of bleeds, procedures, hospitalizations, study drug(s) usage, and other medications. Source data will be stored at the HTC in a locked file cabinet in a locked room.

Laboratory Specimens. A 3.8 ml (¾ tsp) blood sample, including a citrate (plasma) tube and a heparin (PBMC) tube will be drawn on all subjects at baseline, week 4, 12, 24, 36, and 48 of the trial. All samples will be drawn before administration of the study drug(s). All assays in the study are validated for small pediatric volumes, so total blood draw is 22.8 ml (4½ tsp) over the 48-week study for the anti-FVIII by chromogenic Nijmegen-modified Bethesda (CBA) assay, FVIII-specific T cell ELISPOT assay, trough FVIII (chromogenic assay), HLA, hemophilia genotype, and sample for storage (See Appendix, Table). De-identified plasma (citrate) blood samples will be processed, frozen, and shipped to a repository under the direction of [name], Coagulation Laboratory, Vitalant, Pittsburgh PA. The inhibitor (anti-FVIII) by chromogenic Nijmegen Bethesda assay (CBA) will be run real time on citrate plasma samples, with confirmation on stored aliquots for those testing positive (anti-FVIII > 0.6 B.U.). The hemophilia genotype and HLA type will be performed on buffy coat from the citrate sample at baseline only, and the FVIII trough by chromogenic assay will be run on an aliquot of the citrate sample. Samples for future testing will be stored up to 5 years after the end of the study. De-identified heparinized samples (PBMC) will be sent to the laboratory of [name], Uniformed Services University of the Health Sciences (USUHS), Bethesda, MD. The PBMC sample will be snap frozen in dimethyl sulfoxide (DMSO) and stored in liquid nitrogen until batch testing for FVIII-specific T cell responses by ELISPOT assay. Samples for future testing (hemophilia genetic and immunology studies) will be stored indefinitely after the end of the study. Any part of subject blood samples that remains after the planned blood tests are done will either be destroyed or all identifiers and means of linking it back to the subject will be permanently removed prior to sending to repository for storage. The remaining sample will be used only for genetic and immunologic studies related to inhibitor development and hemophilia. The stool sample will be collected by patients at home, placed in a tube, and returned in a container to Vitalant, and transported locally to VMI, Pittsburgh PA.

